2.6.2. Safety Variables

Safety assessments performed during the study included physical examinations, measurement of vital signs, 12-lead electrocardiograms (ECGs), clinical laboratory evaluations including hematology, serum chemistry, and urinalysis, and monitoring of adverse events.

3. SUBJECT POPULATIONS

3.1. Population Definitions

The following subject populations will be evaluated and used for presentation and analysis of the data:

- The Roll-In (RI) population will consist of all patients enrolled in a non-blinded roll-in manner and remained eligible to receive the Phagenyx treatment after initial pre-procedural VFSS testing is completed and the PAS is determined to meet entry criterion and no exclusions are found. All patients in whom treatment was attempted, regardless of procedural outcome, will be included in this analysis set.
- The **Safety Population** will consist of all patients that were enrolled in the study (including Roll-In patients) and underwent the pre-procedural VFSS with or without subsequent placement of the Phagenyx Catheter.
- The **Intent to Treat (ITT)** Population will consist of all patients that were randomized, irrespective of their protocol adherence and continued participation in the study.
- The **Per Protocol (PP) Population** will consist of all randomized patients who completed the full Phagenyx treatment regimen according to their randomization assignment and for whom completed primary endpoint data are also complete.

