The VFSS is considered the "gold standard" in the US for diagnosing the nature and severity of dysphagia as well as providing feedback on the effects of dysphagia therapy²¹. Hence, it would not be unusual for a dysphagic patient to undergo at least two VFSS studies over the course of being treated for dysphagia after stroke. The investigational protocol specifies two VFSS assessments be performed within a 1-week period to standardize baseline measures and to provide feedback on the dysphagia treatment under investigation shortly after the intervention. Patients typically undergo a non-instrumented dysphagia assessment before referral for an instrumented VFSS. Participating sites will be instructed to use the study-specific VFSS protocol for patients referred to an instrumented dysphagia assessment if they also appear to meet the rest of the study inclusion/exclusion criteria. Patients meeting the study criteria will require one subsequent VFSS performed according to the study-specific VFSS protocol. Hence, patients will be exposed to one, and possibly two, more VFSS than they would if they were not enrolled in this study.

The VFSS imparts a small dose of ionizing radiation. Zammit-Maempel et. al., reported a median exposure time of 171 seconds and an associated dose of 0.20 milliSieverts or mSv⁴³, while Moro and Cazzani reported a median exposure time of 149 seconds and

CONFIDENTIAL Page 26 of 71

an associated dose of $0.35~\text{mSv}^{44}$. The standardized VFSS protocol proposed for this study is associated with an average duration of 2.9 minutes radiation exposure (95% confidence interval 2.8-3.0 minutes). Extrapolating from the relationship Moro and Cazzani published, the VFSS time of 2.9 min (174 sec), relates to an effective dose of $\sim 0.44 \text{mSv}^{45}$.

Table 1 provides background information on relative average absorbed doses of ionizing radiation that a person would experience when exposed to various sources. On average, a U.S. resident receives an annual radiation exposure from natural sources of about 3.1 mSv. In addition, man-made sources of radiation from medical, commercial and industrial activities contribute roughly 3.1 mSv more to our annual exposure⁴⁶. Computed tomography (CT) scans, are among the largest of these sources, with a head CT contributing 2mSv⁴⁷.

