3 STUDY OBJECTIVES AND ENDPOINTS

STUDY OBJECTIVES	STUDY ENDPOINTS		
Primary			
To evaluate the efficacy of Phagenyx® treatment in reducing the severity of unsafe swallows.	Swallowing safety of a bolus based on PAS of each swallow, determined by a VFSS 48 hours after completion of investigational treatment, converted to a trichotomized ordinal response of safe (PAS 1-3), penetration (PAS 4-5), or aspiration (PAS 6-8). Each patient contributes up to 12 post-treatment repeated measurements (PAS) including 6 swallows of thin and 6 swallows of nectar.		
Secondary			
To evaluate the efficacy of Phagenyx treatment in improving nutritional management.	Functional Oral Intake Scale (FOIS) at 7 days following the last investigational treatment.		
	Dysphagia Severity Rating Scale (DSRS) at 7 days following the last investigational treatment		
Exploratory			

CONFIDENTIAL Page 30 of 71

STUDY OBJECTIVES	STUDY ENDPOINTS
To further characterize the efficacy of Phagenyx® treatment in reducing the severity of unsafe swallows.	The severity of unsafe swallows will be further evaluated via: O PAS outcome by each consistency (thin and nectar) O Physiologic measurement obtained using the Modified Barium Swallow Impairment Profile (MBSImP) metrics will be extracted from the thin and nectar swallows by the core lab by using the baseline and follow up VFSS data. These validated and reliable metrics of critical swallowing movements will be explored for their relationship to the primary study endpoint (PAS). O PAS dichotomized as safe (PAS 1-3) or
To evaluate the efficacy of Phagenyx® treatment on nutritional management changes.	unsafe (PAS 4-8) Nutritional management improvement will be evaluated via: Dysphagia Severity Rating Scale (DSRS) at 14 days or discharge, whichever is first, and at 11 weeks following the last investigational treatment. Time from baseline to removal of enteral feeding (i.e., removal of NG tube or PEG or transition to oral feeding, or first diet upgrade) Functional Oral Intake Scale (FOIS) at 7 days, 14 days or discharge, whichever is first, and 11 weeks following the last investigational treatment
To evaluate the efficacy of Phagenyx® treatment on improving quality of life.	Quality of life (QOL) will be assessed baseline and 11 weeks following the last investigational treatment via the following instruments: o EuroQoL-5 Dimension Questionnaire (EQ-5D) and EuroQoL-Visual Analogue Scale (EQ-VAS)

CONFIDENTIAL Page 31 of 71

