7 VFSS STOPPING CRITERIA AND PATIENT/SITE/STUDY TERMINATION

7.1 VFSS STOPPING CRITERIA

• If the PAS is ≥ 6 (see below) for three consecutive bolus trials of the same consistency, that consistency should be stopped and the investigator (or trained and authorized designee) can decide if it is safe to move to the next consistency to assess dietary modification, or if the study needs to be stopped.

Penetration Aspiration Score Definitions:

- Score = 6: Material enters the airway, passes below the vocal folds and is ejected into the larynx or out of the airway.
- Score = 7: Material enters the airway, passes below the vocal folds & is not ejected from the trachea despite effort
- Score = 8: Material enters the airway, passes below the vocal folds & no effort is made to eject
- A 'Stop' may be applied at any time if the Investigator (or trained and authorized designee) feels it is unsafe for the patient to continue.
- If VFSS time exceeds 3 minutes, the procedure must be stopped.

Regardless of completion of the PES treatment, patients will be encouraged to remain in the study until they have completed the protocol-required follow-up period while maintaining respect for all patient rights. Patients are free to withdraw from participation in the study at any time upon request.

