4.8. Efficacy Evaluation

4.6.1 Primary Efficacy Analysis

The primary endpoint is trichotomized PAS on each bolus, determined by VFSS 48 hours (+/- 24 hours) after completion of PES treatment. The three ordinal PAS categories are defined as Safe (PAS 1-3), Penetration (PAS 4-5), and Aspiration (PAS 6-8). Each patient contributes 12 measurements to the primary endpoint, of which six are from boli of a thin consistency and 6 are from boli of a nectar consistency.

The ITT population will be used for the primary analysis.

A cumulative logistic model will be used to analyze the primary endpoint, and a sandwich variance estimator via a generalized estimating equations approach will be used to account for correlated PAS outcomes within each patient.

The statistical model for the primary analysis will include treatment, bolus consistency, baseline maximum PAS, and treatment by consistency interaction as predictors. The response of individual i on bolus t is coded as $y_{it} = 1$ for a safe swallow, $y_{it} = 2$ for a swallow resulting in penetration, and $y_{it} = 3$ for a swallow resulting in aspiration. The log odds of a swallow with response $\leq j$ conditional on predictors x_{it} is modeled as

$$logit(P(y_{it} \le j | x_{it}))$$

$$= \beta_j + \beta_{base} * base_{it} + \beta_{trt} * trt_i + \beta_{nectar} * nectar_t + \beta_{trt*nectar} trt_i * nectar_t$$

with ordered intercept terms $\beta_1 < \beta_2$, a treatment indicator trt_i (1=PES, 0=control), and a consistency indicator $nectar_i$ (1=nectar, 0=thin). The maximum PAS (1-8) of individual i across all pre-treatment swallows of a given consistency at baseline is denoted $base_{it}$. The GEE approach with robust sandwich estimator is used to account for within subject correlation.

Missing PAS data will be imputed in the primary analysis. PAS values that are missing due to application of VFSS stopping criteria will be assigned the worst (highest) post-treatment PAS value. For patients who have no post-treatment PAS data due to lost-to-follow-up or death, the post-treatment PAS values will be imputed from baseline PAS values and other patient baseline characteristics using multiple imputation. In addition, tipping point analysis will be performed as a sensitivity analysis.

The estimated treatment effect in the logistic model will be presented along with standard error. The treatment effect will also be presented as an odds ratio with 95% confidence interval.

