Sensitivity analysis will be performed in which missing values are ignored. Analyses of the primary endpoint with and without imputation will also be performed on the per protocol population.

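### Per-protocol set: primary data must be complete, a term left undefined; read with SAP 4.6.1, this drops patients whose exam was stopped for aspiration and empties the planned PP imputation comparison

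*SAP*

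**What the plan says.** **PP set.** SAP 3.1 and Protocol 9.3 use the same wording. A randomized patient enters PP after completing the assigned treatment course, and only if it is someone "for whom completed primary endpoint data are also complete". Neither document says what complete means.

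**Number of measurements.** SAP 4.6.1 (printed under 4.8) says "Each patient contributes 12 measurements to the primary endpoint", six thin and six nectar. Protocol 9.4.2 gives the same count. Protocol section 3 and the synopsis are looser: "Each patient contributes up to 12 post-treatment repeated measurements".

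**Stopping an exam.** Under Protocol 7.1, if PAS is 6 or higher "for three consecutive bolus trials of the same consistency, that consistency should be stopped". The investigator may also stop at any time, and "If VFSS time exceeds 3 minutes, the procedure must be stopped".

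**Missing boli.** SAP 4.6.1 classes PAS 6-8 as aspiration, the worst of the three outcome categories. It describes values lost to the stopping criteria as missing and fills them with the patient's worst post-treatment score. Patients with no post-treatment PAS at all, through loss to follow-up or death, are multiply imputed.

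**Planned PP analyses.** SAP 4.6.1 adds: "Analyses of the primary endpoint with and without imputation will also be performed on the per protocol population".

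**The concern.** A patient can receive all three sessions, attend the follow-up VFSS, aspirate on three boli in a row and have that consistency ended early. On a literal reading, the patient then leaves PP because of the aspiration, not because of poor adherence. If PES reduces aspiration, more control than PES patients leave, and the controls who remain are the better swallowers.

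PP is the only population other than ITT in which the SAP plans to analyze the primary endpoint. An analysis meant to support the ITT result would be weakened by the construction of its own population. The comparison meant to show how much the fill rule matters would show nothing.

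**Working it through.** The plan states no size for the PP set and no follow-up aspiration rate, so there is no figure of its own to reproduce. The two structural points need only the text. The size needs assumptions.

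**1. Who leaves PP.** Complete primary data means 12 boli (SAP 4.6.1). A stop triggered on bolus 3, 4 or 5 of a consistency leaves later boli ungiven, and SAP 4.6.1 calls those values missing. The data are then not complete. A run of three that ends on bolus 6 leaves nothing missing, so that patient stays. No section exempts stopped exams.

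**2. What imputation can act on in PP.**

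| SAP 4.6.1 rule | Applies to | In a complete-data PP set? |
|---|---|---|
| Worst-value fill | Boli lost to the stopping criteria | No |
| Multiple imputation | Patients with no post-treatment PAS | No |

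Both groups are absent, so the two PP analyses coincide. This needs no assumption about rates.

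**3. Hand check on exclusion.** Let p be the chance of aspiration on each bolus, independent across boli. The chance that a run of three is completed by bolus 5 is p³ + 2(1 − p)p³ = p³(3 − 2p). The values of p below span the control aspiration shares in step 4.
- p = 0.17: 0.004913 × 2.66 = 0.013 per consistency; over two consistencies, 1 − (1 − 0.013)² = 0.026.
- p = 0.44: 0.085184 × 2.12 = 0.181 per consistency; over two, 1 − (1 − 0.181)² = 0.329.

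The simulated rates below are higher mainly because swallows within a patient are correlated.

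**4. Simulation.** Design: 100,000 patients per arm and six thin plus six nectar boli. Model: logit P(Y ≤ j) = θ_j + u + b·PES + c·nectar, with a normal patient intercept u. Only the three-in-a-row rule removes boli. Fit: pooled cumulative logit with treatment, nectar and their interaction, omitting baseline PAS; the odds ratio shown is for thin liquid. From the SAP: odds ratio 2.23 (4.2). *Assumed, not in the documents:* nominal control thin-liquid share safe 30-60%, penetration 20%, intercept SD 1-3, nectar log odds +0.5.

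| Safe share / SD | Excluded, control | Excluded, PES | OR, all 12 boli seen | OR, literal PP | Control aspiration share, all → PP |
|---|---|---|---|---|---|
| 30% / 1 | 38.6% | 16.3% | 2.17 | 1.70 | 44.1% → 30.6% |
| 30% / 3 | 43.1% | 24.7% | 2.11 | 1.57 | 44.1% → 15.9% |
| 40% / 2 | 31.1% | 14.5% | 2.14 | 1.66 | 35.2% → 18.3% |
| 50% / 2 | 21.1% | 8.5% | 2.15 | 1.74 | 26.2% → 14.6% |
| 60% / 1 | 6.9% | 1.6% | 2.21 | 2.03 | 17.0% → 14.5% |
| 60% / 3 | 14.4% | 5.7% | 2.20 | 1.86 | 17.4% → 8.0% |

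All twelve settings (four safe shares by three SDs) lie between the extremes of this table for exclusions and odds ratios. PP with imputation minus PP without is exactly 0 in each. With no treatment effect, exclusions agree between arms to within 0.2 percentage points and the PP odds ratio is 0.99-1.00.

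**5. Bias versus lost patients.** Assume information per retained patient is unchanged.
- 30% / 3: the effect shrinks by ln 1.57 / ln 2.112 = 0.60. Lost patients alone scale Z by √[2 / (1/0.569 + 1/0.753)] = 0.81. Together: 0.49.
- 60% / 1: ln 2.025 / ln 2.205 = 0.89, and √[2 / (1/0.931 + 1/0.984)] = 0.98. Together: 0.87.

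**The case against.** The strongest reply is that the strict reading was not intended. The PP sentence is garbled and never says all 12 boli. Protocol section 3 foresees fewer than 12. An exam stopped under Protocol 7.1 is a protocol-compliant exam, and after the worst-value fill the patient's data could be called complete. Planning PP with and without imputation presupposes patients with something to impute. If complete only means that a follow-up VFSS took place, neither problem arises.

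This stands as evidence of intent. It does not settle the text. Neither document states the softer meaning, and SAP 4.6.1 itself calls the stopped boli missing. Two sections therefore conflict, and whoever programs the PP set must choose between two materially different populations. SAP 3.2 does not help, since it only allows further removals for major violations.

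Three stronger inferences are tempting and not supported:
- *The trial's conclusion is at risk.* The primary analysis is ITT, and no interim, sample-size or success rule in SAP 4.4-4.5 uses PP. In the illustration the selection creates no effect where there is none.
- *PP would contradict a positive ITT result.* That depends on assumed aspiration rates. Step 5 gives a Z between about half and nearly nine-tenths of its full-set value, and part of each fall is lost sample size, not bias.
- *Everyone with three consecutive aspirations leaves.* Only those with boli left ungiven do.

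The time limit and discretionary stops also make data incomplete, for reasons only partly tied to outcome. Protocol 2.4.1 expects an "average duration of 2.9 minutes radiation exposure" against a three-minute limit, so time stops could be common. The documents give no spread of individual times, and these stops are not in the figures above.

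**Conclusion.** The point holds as a defect in a supportive analysis. As written, the PP definition selects on the outcome and conflicts with the PP imputation comparison in SAP 4.6.1. The empty comparison follows from the wording under the 12-bolus reading, whatever the rates.

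The direction of the bias, toward no effect when PES works, rests on PES lowering aspiration. Its size is illustrative: about 7-43% of control and 2-25% of PES patients excluded, and an odds ratio of about 2.1-2.2 reduced to about 1.6-2.0. That range rests on the assumed control swallow distribution, within-patient correlation and nectar effect. It would shift with the true rates and with time or discretionary stops. The correction is worth making because it is cheap and removes a choice that might otherwise be made after data are seen.

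**What to change.** In Protocol 9.3 and SAP 3.1, define PP as randomized patients who completed the assigned regimen, have no major violation as determined under SAP 3.2, and have a follow-up VFSS with at least one scored bolus. State that boli not given because of the VFSS stopping criteria do not make the data incomplete.

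In SAP 4.6.1, say that the PP analysis is run once with the worst-value fill and once on observed boli only. The fill must not be carried into the second run, because it is itself an imputation.

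The stopping rule then excludes nobody from PP. Under the assumptions above, and before any adherence exclusions, the two runs give odds ratios of 2.14-2.30 and 1.97-2.17, so the comparison has content. Dropping every endpoint-data requirement would go further than needed: it would bring patients with no follow-up VFSS into PP through multiple imputation.

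The cost is a sentence or two in each document, with no change to any clinical procedure, sample size or primary analysis.

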3.2. Protocol Violations

At the discretion of the sponsor, major protocol violations as determined by a review of the data prior to unblinding of the study results and the conduct of statistical analyses may result in the removal of a subject's data from the PP Populations. The sponsor, or designee, will be responsible for producing the final protocol violation file (formatted as a Microsoft Excel file), in collaboration with Cytel and the data monitoring group as applicable; this file will include a description of the protocol violation, and clearly identify whether or not this violation warrants exclusion from the PP Population. This file will be finalized prior to hard database lock.

All protocol violations will be presented in the data listings.

4. STATISTICAL METHODS

4.1. Statistical Hypotheses

The primary efficacy analysis is based on an ordinal logistic model of PAS (1-8 scale) of each bolus, determined by VFSS 48 hours following the last investigational treatment, and converted to a trichotomized response as follows: Safe (PAS 1-3), Penetration (PAS 4-5), or Aspiration (PAS 6-8). Hypothesis testing will be a superiority test performed on the main effect of treatment, β_{trt} , i.e., the difference in cumulative log odds between treatment groups, with $\beta_{trt} > 0$ indicating the PES group has higher odds of a safer responses than the control group.

- Primary Efficacy Endpoint: The null hypothesis is that $\beta_{trt} \leq 0$ (PES does not result in safer swallows than the control treatment), and the alternative hypothesis is that $\beta_{trt} > 0$ (PES results in safer swallows than the control treatment).
- If the primary endpoint meets statistical significance then formal testing and analysis for the secondary endpoint will be carried out.

The analysis of the secondary endpoint of FIOS is based on a Cochran-Mantel-Haenszel (CMH), stratified by site and baseline PAS, using the modified ridit score and test of "row mean scores different" to take into account the ordered nature of the response.

The analysis of the secondary endpoint of DSRS is based on an ANCOVA model of mean DSRS 48 hours after the last study treatment, adjusting for baseline. Hypothesis testing will be a superiority test performed on the main effect of treatment, δ , with $\delta \ge 0$ indicating the PES group has lower mean DSRS than the control group.

• Secondary Efficacy Endpoint of DSRS: The null hypothesis for the $\delta \leq 0$ (PES does not result in lower DSRS), and the alternative hypothesis is that $\delta > 0$ (PES results in lower DSRS).

4.2. Sample Size Justification

Sample size and power was determined through simulations. The study will follow an adaptive group sequential design with unblinded sample size re-assessment. In order to assure 180 evaluable patients with 7 day (+/- 1day) data and assuming a 20% dropout rate, approximately 225 patients will be enrolled initially. An interim analysis for futility (non-binding stop) will occur after the first 60 patients complete their 7 day visit, and another interim analysis will be performed for efficacy after 120 patients for futility stopping, early efficacy stopping on the primary endpoint and secondary endpoint, and sample size re-assessment (SSR). The total sample size may be increased up to approximately 338 patients after the second interim analysis to ensure up to 270 evaluable patients.

Based on prior feasibility studies (Bath et al., 2016) the primary endpoint is hypothesized to have an odds ratio of 2.23 favoring the PES group. For the secondary endpoint, the difference in mean DSRS between treatment groups is expected to be 1.75. A common standard deviation of 4 is assumed for DSRS in both treatment groups. With these effect sizes, the power is 95% for significance on the primary endpoint and 85% for significance on both endpoints. Additional simulation results under different assumptions are provided in the Simulation Report.

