9.4.3 ANALYSIS OF THE SECONDARY EFFICACY ENDPOINTS

The secondary efficacy endpoints will be tested for statistical significance sequentially provided the primary endpoint is found to be statistically significant. The ITT population will be used. The first endpoint tested will be FOIS at 7 days following the last investigational treatment. The second endpoint tested will be DSRS at 7 days following the last investigational treatment.

Analysis details are specified in the SAP.

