4.5.3. Procedure at the second interim analysis

The second interim analysis is planned for when for when 120 patients complete their 7 day visit.

Efficacy stopping: An early efficacy stopping boundary of Z > 2.5093 (one-sided P < 0.0060) will be used for all efficacy endpoints. This boundary is the group sequential boundary derived from the Lan-DeMets O'Brien Fleming spending function at 2/3 information fraction. Early stopping for efficacy will be recommended only if both the primary endpoint and secondary endpoint cross the same boundary. If the study continues, both endpoints will be tested against the group sequential boundary 1.9929 at the final analysis in a sequential manner -- the secondary endpoint is tested if the primary endpoint reaches statistical significance -- to preserve the study-wise type 1 error rate at one-sided level 0.025.

If the study is not stopped for efficacy, the interim results will be classified into different zones depending on estimation of the conditional power on the primary endpoint and, separately, on the secondary endpoint. Based on the interim zone, one of the following actions will be recommended:

- Stop the study for futility (non-binding stop).
- Continue the study until reaching the planned 180 evaluable patients (approximately 225 enrolled).
- Continue the study and increase the sample size up to a maximum of 270 evaluable patients (approximately 338 enrolled).

Details on the boundaries of these interim zones and specific actions to be taken within these zones are deferred to a restricted Simulation Report whose circulation is limited to a core study team to include the ISC and DMC in order to minimize the possibility of operational bias.

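### The 85% power in SAP 4.2 covers the primary endpoint and DSRS only, while the protocol tests FOIS before DSRS and no FOIS power is given

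*SAP*

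**What the plan says.** **Power.** SAP 4.2 states that "Sample size and power was determined through simulations". The design is adaptive, with 180 evaluable patients planned and up to 270 after sample size re-assessment (SSR). Two effects are given. For the primary, "the primary endpoint is hypothesized to have an odds ratio of 2.23 favoring the PES group". For DSRS, "the difference in mean DSRS between treatment groups is expected to be 1.75", and "A common standard deviation of 4 is assumed for DSRS in both treatment groups". The result is: "With these effect sizes, the power is 95% for significance on the primary endpoint and 85% for significance on both endpoints". SAP 4.2 treats DSRS as the secondary endpoint and gives nothing for FOIS. Protocol 9.2 gives power for the primary only.

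**Test order in the protocol.** Protocol 9.4.3 tests the secondary endpoints sequentially once the primary is significant: "The first endpoint tested will be FOIS at 7 days following the last investigational treatment". DSRS at 7 days comes second.

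**Test order in the SAP.** SAP 4.5.3 says that "both endpoints will be tested against the group sequential boundary 1.9929 at the final analysis in a sequential manner", and explains this as testing the secondary if the primary succeeds. It has a single secondary endpoint in view, and SAP 4.5.1 shows that this is the one analysed by ANCOVA, namely DSRS. SAP 4.6.2 (printed under 4.8) names both FOIS and DSRS as secondary, makes DSRS conditional on the primary only, and puts the two in no order. SAP 4.1 describes both analyses, also without an order. SAP 5 says that the planned analyses have not changed from the protocol.

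**The concern.** A power figure describes a particular sequence of tests. The 85% describes two: primary, then DSRS. In the protocol's sequence DSRS is the third test, so a patient sample that gives significant results on the primary and DSRS but not on FOIS supports no formal DSRS claim. The 85% counts such a sample as a success.

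This matters because nutritional management is the only secondary objective, and DSRS is the secondary endpoint that the plan is built around: Protocol 9.2 uses it, with the primary, to drive SSR, and the SAP appears to require it for early efficacy stopping. A reader who takes the protocol's order and the SAP's power together may overestimate the chance of a formal DSRS claim. Until the documents agree on the order, it is also unclear which sequence the power figure should describe.

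**Working it through.** **1. The plan's own figures.** The enrolment numbers reproduce: 180/0.8 = 225 and 270/0.8 = 337.5, rounded to 338. The 85% cannot be reproduced exactly, because the SSR zones, the correlation between endpoints and the PAS distribution are not in the documents. It can be bracketed (steps 3 to 5).

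**2. Power for the protocol's sequence.** All three tests must succeed, so

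P(primary, FOIS and DSRS) ≤ min{P(primary and DSRS), P(FOIS)} = min{85%, FOIS power}.

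If FOIS is independent of the other two, the probability is 0.85 × FOIS power. The FOIS powers below are assumptions, since the documents give none.

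| Assumed FOIS power | All three, FOIS independent | Upper bound |
|---|---|---|
| 60% | 0.85 × 0.60 = 51.0% | 60% |
| 70% | 0.85 × 0.70 = 59.5% | 70% |
| 80% | 0.85 × 0.80 = 68.0% | 80% |
| 90% | 0.85 × 0.90 = 76.5% | 85% |

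Positive correlation moves the result from the middle column towards the right-hand one.

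**3. Two endpoints at a fixed 180, without SSR.** Inputs: difference 1.75 and SD 4 (SAP 4.2), SD taken as residual; 90 per arm (1:1 allocation assumed, as no ratio is stated); final boundary 1.9929 (SAP 4.5.3).

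- Expected Z for DSRS = 1.75 / (4 × √(4/180)) = 1.75 / 0.5963 = 2.935.
- DSRS power = Φ(2.935 − 1.9929) = Φ(0.942) = 82.7%. At 1.96 it is 83.5%.
- With primary power of 95%, joint power is 0.95 × 0.827 = 78.6% under independence, and 81.4% at an endpoint correlation of 0.7.

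**4. Two endpoints with SSR.** At 270 patients the expected DSRS Z is 1.75 / (4 × √(4/270)) = 3.594, which gives Φ(1.602) = 94.5%. The adaptive design was simulated with combination weights of 2/3 and 1/3 on the variance scale, an interim boundary of 2.5093 required on both endpoints, a final boundary of 1.9929, primary power of 95% at 180 and endpoint correlation of 0 to 0.6. Futility stopping was assumed at conditional power below 5% at the second look. N was assumed to rise to 270 when conditional power lay between 30% and 90%:

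| Assumed driver of the increase | Joint power |
|---|---|
| Primary | 82% to 85% |
| DSRS | 84% to 86% |
| Both at least 30%, one below 90% | 85% to 86% |
| Either | 86% to 89% |

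If the 95% is itself a figure with SSR, primary power at 180 would be lower. With 93% at 180, the overall range is 81% to 88%.

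**5. Two endpoints at 180 if SD 4 is the raw SD.** SAP 4.6.2 adjusts DSRS for its baseline, so the residual SD is 4√(1 − r²).

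- r = 0.4 (assumed): expected Z = 2.935/0.9165 = 3.202; DSRS power 88.7%; joint 0.95 × 0.887 = 84.2%.
- r = 0.5 (assumed): expected Z = 2.935/0.8660 = 3.389; DSRS power 91.9%; joint 0.95 × 0.919 = 87.3%.

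**The case against.** A reader might infer from step 3 that the 85% is an arithmetic error, since joint power cannot exceed the 82.7% for DSRS alone. The documents do not support this. SAP 4.2 obtains power by simulating an adaptive design that can grow to 270, and it does not tie the 85% to a fixed 180. Plausible SSR rules give 85%. Nor is the sample size increase the only route: ANCOVA adjustment could reach about 85% at 180 if the SD is raw. Writing 79% to 81% into the SAP as the corrected value could replace a valid number with a wrong one.

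Two further defences deserve weight. SAP 4.5.3 sends the SSR zones to a restricted Simulation Report available to the independent statistical center and the DMC, so those groups have detail that the public documents lack. That is a sound reason to withhold the zone boundaries, but it does not prevent labelling the figure as with or without SSR. Secondly, under the SAP's own order a two-endpoint figure is the right one for a DSRS claim. That is true, but Protocol 9.4.3 states a different order and SAP 5 says that nothing has changed, so the conflict remains.

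Finally, the FOIS powers in step 2 are not estimates from the plan. FOIS and DSRS both reflect oral intake and may well be positively correlated, which would put the result above the independent case.

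**Conclusion.** The 85% is not the power of the protocol's own test sequence. Under Protocol 9.4.3 a formal DSRS claim has power of at most 85% and at most the FOIS power, and the latter is unknown. The upper bound rests on the stated 85% and on reading sequential testing in the usual way, with each test requiring success on the one before. The illustrative 51% to 77% further assumes FOIS power of 60% to 90% and independence, and should not be read as the trial's actual power.

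For the two-endpoint adaptive design, the 85% is not shown to be wrong. It is unlabelled: depending on whether SSR is counted and what SD 4 means, the same inputs give about 79% to 89%. The calculations use the 1.9929 boundary of SAP 4.5.3. SAP 4.5.4 prints 2.5093 for the final test, which is a separate inconsistency.

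**What to change.** 1. Agree one order for the primary, FOIS and DSRS, and state it identically in Protocol 9.4.3 and SAP 4.1, 4.5.3 and 4.6.2. If DSRS directly follows the primary, the two-endpoint figure covers the DSRS claim and FOIS needs its own defined place.
2. Restate power in SAP 4.2 for the agreed sequence, with an explicit FOIS effect and its assumed correlation with the other endpoints.
3. Label the 85% as with or without SSR, give the companion figure at 180 without SSR, and say whether SD 4 is raw or residual after ANCOVA. The zone boundaries can stay in the restricted report.

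The cost is a text correction in both documents, one FOIS assumption and a rerun of the existing simulations. The stated power may become less favourable. No change in enrolment is needed.
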